3 INVESTIGATIONAL PLAN

3.1 Overall Study Design and Plan

This is a prospective, open-label, multicenter study designed to evaluate the predictive capacity of Tc 99m tilmanocept planar imaging for downstream clinical response(s) in individuals with moderate to severe RA who are candidates for change in anti-TNF α therapy. Temporal (Baseline to 5-week) changes in quantitative imaging will be correlated with longitudinal (Baseline to 12- and 24-week) assessments of clinical RA outcomes to evaluate the clinical utility of Tc 99m tilmanocept for the expedited evaluation of antirheumatic treatment efficacy when compared with longitudinal assessments in clinical practice.

Prior to the initiation of a new therapy, subjects will undergo baseline rheumatological evaluations of ACR/EULAR 2010 Classification Criteria, CDAI, DAS28, HAQ-DI[©], and a serological RA panel for the characterization of disease activity. Following these evaluations, subjects will receive an IV dose of 150 mcg tilmanocept radiolabeled with 10 mCi of Tc 99m and undergo baseline planar imaging of the bilateral hands and wrists beginning 60-75 minutes following Tc 99m tilmanocept administration. Upon completion of baseline imaging procedures, subjects will commence a new anti-TNF α bDMARD treatment regimen and return to the clinic 5 \pm 1 weeks later for a series of rheumatological evaluations (including CDAI, DAS28, ACR Response Criteria, and HAQ-DI[©]), drug administration, and bilateral hand/wrist imaging. The rheumatological evaluations will be repeated at 12 \pm 1 weeks and 24 \pm 1 weeks after commencement of the new therapy.

Images will undergo centralized quantification for the derivation of joint-specific and global tilmanocept uptake values (TUV). At the joint level, TUV is defined as the intrasubject ratio of the average pixel intensity of a joint to the average pixel intensity of the reference region. TUV_{global} is a per subject summary of TUV_{joint} values greater than the upper 95th percent (2 standard deviations) of the normative database representing RA-specific inflammation. TUV calculations are additionally described in the Statistical Analysis Plan.

All images will be read by three nuclear medicine specialists trained in the reading of these images. Each reader will work independently of the other readers and will be blinded to clinical assessments. Each reader will provide both a qualitative read and map regions of interest for calculation of TUVs.

Temporal differences in TUV_{global} from baseline to 5 ± 1 weeks of therapy ($\Delta TUV_{global[5w]}$) will be compared with longitudinal clinical outcomes at 12 ± 1 and 24 ± 1 weeks of therapy defined by changes in CDAI ($\Delta CDAI_{12/24w}$), changes in DAS28 ($\Delta DAS28_{[12/24w]}$), and assessment of ACR Response Criteria ($ACR_{12/24w}$) to evaluate the efficacy of TUV_{global} for the accelerated prediction of clinical response to antirheumatic drugs.

Tc99 tilmanocept images with low levels of localization in the joints- and thus presumptively low numbers of synovial lining macrophages are thought to be less likely to respond to anti-TNF α therapies, and these cases will be classified as predicted non-responders using their baseline scan alone. The determination of low level of localization is done quantitatively by

applying a threshold TUV_{global} of 5 as the cutoff value. Patients whose baseline scans are determined to have TUV_{global} below this are predicted to be non-responders. This value was determined in the completed Phase 2B trial NAV3-31. Patients whose TUV_{global} scores are 5 or above then have their baseline scans compared to their Week 5 scans to determine if they will be classified as predicted responders or non-responders. A quantitative analysis of their change in TUV_{global} score from baseline to Week 5 is performed to see if their levels of localization have changed significantly. All subjects in this trial will undergo baseline and Week 5 scans, including those whose baseline scans demonstrate TUV_{global} below 5, as an objective is to assess if any longitudinal changes in TUV_{global} from baseline to Week 5 can be predictive of clinical response or non-response. The process of dichotomizing subjects based on their baseline TUV_{global} scores is referred to as bucketing. Statistical analyses will be performed on bucketed data. In the bucketed analyses, subjects with baseline TUV_{global} below 5 are classified as predicted non-responders while those with baseline TUV_{global} above 5 are classified as either predicted responders or non-responders based on the change in TUV_{global} between baseline and Week 5.

The Schedule of Events (Appendix 1) contains a list of all study procedures and time points. Study activities are described in detail in Section 7.

3.2 Protocol Adherence

Strict adherence to all specifications outlined in this protocol is required for all aspects of the study conduct; the investigator may not modify or alter the procedures described in this protocol. If protocol modifications are necessary, all alterations that are not solely of an administrative nature require a formal protocol amendment for the involvement of Institutional Review Board(s) (IRB(s)).

If an investigator has deviated from the protocol in order to eliminate an immediate hazard to subjects or for other inevitable medical reasons, the investigator shall document all such deviations, including the reasons thereof, and submit the document to the sponsor and the IRB as applicable.

3.3 Study Duration

Subjects will be "on study" for up to 213 days depending on the duration of the screening window (up to 30 days).

4 STUDY POPULATION

The study population will comprise subjects with clinically diagnosed active RA who are candidates for initiation of, or change to, a new anti-TNF α bDMARD regimen. Subjects who meet the eligibility criteria listed below will be eligible for enrollment without regard to other aspects of their disease, such as chronicity of their RA. That is, subjects with newly diagnosed disease, those with chronic disease, and those who have failed multiple therapies will all be eligible for enrollment if they meet the enumerated eligibility criteria.

4.1 Eligibility

Subjects who fulfill all respective inclusion and none of the exclusion criteria will be eligible for enrollment into the study. All inclusion/exclusion criteria must be verified before a subject may be considered eligible for administration of Tc 99m tilmanocept and imaging (Day 0 procedures). A subject will be considered enrolled in the study on the morning of study Day 0 when they arrive at the study site. Written, dated (with time noted) informed consent will be obtained from all subjects. A subject who withdraws consent prior to arrival at the study site on Day 0 will be considered a screen failure.

4.1.1 Inclusion Criteria

Each subject must meet the following criteria to be enrolled in this study.

- 1. The subject has provided written informed consent with HIPAA (Health Information Portability and Accountability Act) authorization before the initiation of any study-related procedures.
- 2. The subject is at least 18 years of age and was ≥ 18 years of age at the time of RA diagnosis.
- 3. The subject is a candidate for initiation of, or change to, a new anti-TNF α bDMARD therapy.
- 4. The subject has RA as determined by the 2010 American College of Rheumatology/European League Against Rheumatism (ACR/EULAR) Classification Criteria (score of $\geq 6/10$).
- 5. The subject has moderate to severe RA as determined by a 28-joint disease activity score (DAS28) of ≥ 3.2 (includes the Erythrocyte Sedimentation Rate [ESR] test and Visual Analog Scale [VAS]).
- 6. Subjects receiving traditional DMARDs must have been on therapy for ≥ 90 days and at a stable dose for ≥ 30 days prior to the first imaging visit (Day 0).
- 7. Subjects receiving bDMARD or janus kinase (JAK) inhibitor therapy must have been at a stable dose > 60 days prior to the first imaging visit (Day 0).
- 8. If the subject is receiving NSAIDS (nonsteroidal anti-inflammatory drug) or oral corticosteroids, the dose has been stable for > 28 days prior to the first imaging visit (Day 0). The corticosteroid dose must be ≤ 10 mg/day of prednisone or an equivalent steroid dose.

4.1.2 Exclusion Criteria

Subjects who meet any of the following criteria will be excluded from the study.

- 1. The subject is pregnant or lactating.
- 2. The subject size or weight is not compatible with imaging per the investigator
- 3. The subject is currently receiving radiation therapy or chemotherapy or has received radiation or chemotherapy within the past 5 years.
- 4. The subject has an active malignancy or a history of malignancy within the past 5 years.
- 5. The subject has had a finger, hand, and/or wrist amputation or hand or wrist joint arthroplasty.
- 6. The subject has renal insufficiency as demonstrated by a glomerular filtration rate of < 60 mL/min.
- 7. The subject has hepatic insufficiency as demonstrated by ALT (alanine aminotransferase [SGPT]) or AST (aspartate aminotransferase [SGOT]) greater than 2 times the upper limit of normal.
- 8. The subject has any severe, acute, or chronic medical conditions and/or psychiatric conditions and/or laboratory abnormalities that would impart, in the judgment of the investigator, excess risk associated with study participation or study drug administration that would deem the subject inappropriate for study participation.
- 9. The subject has a history of hypersensitivity reactions to TNF-inhibitors.
- 10. The subject has a known allergy to or has had an adverse reaction to dextran exposure.
- 11. The subject has received an investigational product within 30 days prior to the Tc 99m tilmanocept administration at the first imaging visit (Day 0).
- 12. The subject has received intra-articular corticosteroid injections ≤ 8 weeks prior to the first imaging visit (Day 0).
- 13. The subject has received any radiopharmaceutical within 7 days or 10 half-lives prior to the administration of Tc 99m tilmanocept at the first imaging visit (Day 0).
- 14. The subject has heart failure (NYHA Class III-IV), a demyelinating disorder, or a chronic/latent infection (e.g., +PPD, HIV, Hepatitis B).

4.2 Recruitment

Subjects will be recruited from rheumatology practices in accordance with the inclusion and exclusion criteria listed above. Potentially suitable subjects will be asked by their treating physician about their willingness to participate in this study. Subjects may also be identified through social media campaigns or advertising.

4.3 Withdrawal

In accordance with the Declaration of Helsinki, each subject is free to withdraw from the study at any time and without providing a reason.

A subject who withdraws consent prior to arrival at the study site on Day 0 will be considered a screen failure.

Should a subject withdraw after administration of the investigational product, all efforts will be made to complete and report the observations up to the time of withdrawal as thoroughly as possible. An explanation should be given of why the subject is withdrawing or being withdrawn from the study.

The investigator may withdraw a subject from the study at any time at the discretion of the investigator for any of the following reasons:

- A protocol violation occurs
- A serious or intolerable AE occurs
- A clinically significant change in a laboratory parameter occurs
- At the investigator's/sponsor's discretion as long as it is in the best interest of the subject
- The sponsor or investigator terminates the study
- The subject requests to be discontinued from the study

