4.4 Replacement

Subjects will be replaced under the following conditions:

• Subjects who did not receive study drug administration or did not proceed to imaging

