9.5 Statistical Analyses

9.5.1 Analysis Populations

The following populations are defined for this study:

Intent-to-Diagnose (ITD) Population – Patients in the safety population meeting the following criteria are members of the ITD population:

- Were injected with Tc 99m tilmanocept at Visit 2 (Day 0)
- Received planar imaging of the hands at Visit 2 (Day 0)

This population will include all patients for whom a prediction might be made, although some patients may be excluded from analysis under this definition if a prediction cannot be made due to missing Day 0 imaging data.

Per-Protocol (PP) Population – The PP population consists of all ITD subjects without major protocol violations.

Safety Population – The safety population includes all subjects who have been enrolled in the study and injected with at least one dose of Tc 99m tilmanocept.

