9.5.3 Analysis of Efficacy Variables

All efficacy analyses will be conducted on both the ITD and PP populations. The ITD population will be the primary analysis set.

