2.3 Missing Data Conventions

In the statistical analysis of the primary efficacy endpoints of the study, missing data will be handled according to the following table of missing data scenarios:

Variable	Scenario	Primary Imputation Rule	Secondary Imputation Rule
Clinical Status at Week 24	Patient discontinued anti-TNFα therapy prior to Week 24 due to non- response to therapy	Patient classified as a clinical non- responder	N/Ă

Clinical Status at Week 24	Patient discontinued study for reasons not attributable to non-response	Clinical status set to missing	Impute mean clinical response*
TUV Prediction	Patient has TUV _{global[b]} that is ≥ 5 but is missing week 5 imaging data	Impute mean prediction**	Prediction is Y (patient has improved)
TUV Prediction	Patient is missing TUV _{global[b]}	Prediction set to missing	N/A

*Mean clinical response will be calculated as follows: calculate the proportion of unique patients whose clinical status is Y (patient is a clinical responder), randomly allocate this proportion of "Y" to the missing clinical status at week 24 values. Assign all other missing clinical status values "N" (patient is clinical non-responder).

**Mean prediction will be calculated as follows: using the patients for whom $TUV_{global[b]} \ge 5$, calculate the proportion whose TUV prediction is Y (patient has improved), randomly allocate this proportion of "Y" to the missing TUV predictions. Assign all other missing TUV predictions "N" (patient has not improved).

To assess the appropriateness of the missing data conventions for clinical status at week 24 and TUV prediction using mean imputation, tipping point analyses will be performed. Specifically, 95% confidence intervals for sensitivity and specificity will be plotted against increasing proportions of missing values imputed as "Y" to see at what point the conclusion of the study is reversed.

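### Section 4.3 allows withdrawal from the study for any protocol violation, so a withdrawn violator's Week 24 ACR50 is avoidably missing from both the ITD and the PP counts

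*Protocol*

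**What the plan says.** Protocol 4.3 gives a discretionary power: "The investigator may withdraw a subject from the study at any time at the discretion of the investigator for any of the following reasons". The first reason listed is "A protocol violation occurs", with no reference to severity. For a subject who leaves after receiving tilmanocept, the section asks that "all efforts will be made to complete and report the observations up to the time of withdrawal as thoroughly as possible"; it does not ask for later visits. Protocol 4.4 limits replacement to "Subjects who did not receive study drug administration or did not proceed to imaging", so a violator who has been dosed and imaged is not replaced.

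The analysis sets treat violations separately. Protocol 9.5.1 says "The PP population consists of all ITD subjects without major protocol violations", and Protocol 9.5.3 says "The ITD population will be the primary analysis set".

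The missing-data table in SAP 2.3 has a row headed "Patient discontinued study for reasons not attributable to non-response". Its primary rule is "Clinical status set to missing"; imputation of the mean clinical response is only the secondary rule. SAP 2.2 accepts that ITD members may be left out of the analysis for lack of imaging or clinical data. The Table 1 shell in SAP Appendix B carries protocol violation as a withdrawal reason, so the route is anticipated.

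**The concern.** The usual purpose of naming an ITD set as primary is to keep violators in the main estimate and let the PP set show what happens without them. Withdrawal from the study undoes that separation for the patients concerned. Someone withdrawn for a violation before Week 24 has no ACR50 status and so cannot be placed in the 2 by 2 table. Because Section 4.3 has no severity threshold, this includes a patient with a minor violation, who by definition belongs in PP and would be lost from the analysed counts of both sets. For withdrawn violators, comparing ITD with PP then says nothing about the effect of violations.

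Under the current schedule (Protocol Appendix 1) no tilmanocept is given after Week 5. What is forfeited by a withdrawal after that point is mainly the reference-standard outcome, which could have been observed.

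**Working it through.** **1. Trace of one patient.** Imaged on Day 0, hence an ITD member (Protocol 9.5.1). Withdrawn for a violation before Week 24 (Protocol 4.3). No later assessment required (4.3); not replaced (4.4). Week 24 status missing under the primary rule (SAP 2.3). Sensitivity is A/T3 and specificity is D/T4 (SAP 4.2.1); both need clinical status, so the patient is in neither. The patient formally remains in ITD; the loss is from the analysed denominator. Clinical status belongs to the patient and not to the reader, so the patient is lost for all three readers.

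**2. The plan's own figures (Protocol 9.4).** Exact one-sided binomial test: r is the smallest count with P(X ≥ r | n, p0) ≤ 0.025, and power is P(X ≥ r | n, p1).

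- Specificity: n = 98, p0 = 0.80, p1 = 0.92. r = 87, actual alpha 0.0158, power 0.908.
- Sensitivity: n = 100, p0 = 0.65, p1 = 0.80. r = 75, actual alpha 0.0211, power 0.913.

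Both agree with the stated 90% for a single reader. Dropout: 100/0.90 = 111.1, rounded up to 112, as stated.

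**3. Loss of numbers.** The documents give no rate of withdrawal for violation. Assume 3% to 10%.

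- Patients: 0.03 × 672 = 20 to 0.10 × 672 = 67.
- Responders: 0.03 × 112 = 3 to 0.10 × 112 = 11. At the upper end 112 − 11 = 101 remain, against 100 required.

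Only if these losses came on top of the planned dropout would the 100 be eroded:

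| Further loss | Responders | Power for sensitivity |
|---|---|---|
| 0% | 100 | 0.913 |
| 2% | 98 | 0.890 |
| 5% | 95 | 0.874 |
| 10% | 90 | 0.880 |
| 15% | 85 | 0.830 |

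The sequence is not monotone because the test is discrete. For specificity, power stays close to 1 at the expected 500 non-responders, even with 15% lost.

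**4. When bias arises.** Let w be the share of clinical responders withdrawn, s the sensitivity in them, and k the sensitivity in those kept. Full sensitivity is (1 − w)k + ws, so the reported value k is in error by w(k − s). The same form holds for specificity among non-responders. If s = k the error is zero, whatever w is. Taking k = 0.80 and w = 0.10, the logical limits s = 1 and s = 0 give errors from 0.10 × (0.80 − 1) = −0.02 to 0.10 × (0.80 − 0) = +0.08. The sign is open.

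**5. What selection could do at the null.** Suppose full sensitivity is exactly 0.65 and w = 0.10, leaving 90 of 100 responders (r = 68). Then k = (0.65 − 0.10s)/0.90.

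- s = 0.65: k = 0.650, single-reader type I error 0.021.
- s = 0.50: k = 0.667, type I error 0.044.
- s = 0.35: k = 0.683, type I error 0.085.

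The values of w and s are assumptions. The results show how the error depends on them; they do not predict it.

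**The case against.** Several objections stand. Withdrawal is optional, so a violator who stays on study keeps the Week 24 outcome, stays in the ITD counts, and leaves PP only if the violation is major. A patient who stopped anti-TNFα therapy for non-response is classed as a non-responder under another row of SAP 2.3 and is not lost. The 10% dropout allowance covers the loss in step 3 if nothing else uses it. SAP 2.3 also provides a secondary imputation for this row and tipping-point plots on Week 24 status, shown for both measures in Figure 6.

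A reader might go further and infer that poor responders are removed selectively and that sensitivity is therefore overstated. The documents do not support this. Sensitivity and specificity condition on clinical status, so losing non-responders as such biases neither. Readers are blinded to clinical assessments (Protocol 3.1) and image results are not to guide care (Protocol 8.4.1), so no route is given by which withdrawal would depend on prediction accuracy. A change in background RA drugs late in the study is a weak example: the stable-dose requirement in Protocol 6.1 runs only through the post-injection safety follow-up, most naturally the telephone visits, the last of them 5 ± 3 days after Visit 4. A sensitivity of 0.40 to 0.65 in withdrawn violators would imply an overstatement between 0.03 × (0.80 − 0.65) = 0.0045 and 0.10 × (0.80 − 0.40) = 0.04, but nothing in the documents supports those values.

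The objections do not remove the gap. The secondary imputation assigns status at random, and the tipping-point plots vary the share imputed as responders. Neither changes the primary rule or recovers an outcome that could have been measured, and the dropout allowance protects numbers, not representativeness.

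**Conclusion.** The point holds as one about avoidable missing primary outcome data. A stated rule permits withdrawal from the study for any violation, and the primary missing-data rule then drops the patient from the analysed counts of both sets. It applies only to violators actually withdrawn before Week 24. Its size is unknown: under an assumed 3% to 10% it costs 3 to 11 of 112 responders, which is within the planned allowance. Bias in either direction, or none, is possible, depending on whether prediction accuracy differs among withdrawn responders or withdrawn non-responders. It would be wrong to conclude that violators in general lose their outcome, or that the primary estimate is shown to be inflated. The change is worth making because it is cheap and removes the question.

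**What to change.** In Protocol 4.3, state that a protocol violation is recorded and classified and by itself affects only PP membership. Add that the scheduled Week 12 and Week 24 clinical assessments, including those needed for ACR50, are still collected from every imaged patient who has not withdrawn consent, even if further imaging or study drug is stopped. The investigator's discretion to stop imaging or study drug need not change.

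In SAP 2.3, state that Week 24 data collected in this way are used in the primary ITD analysis, so that the missing-status row applies only where no assessment was obtained. At the same time, reconcile Protocol 9.5.1, which mentions only absent Day 0 imaging as a ground for leaving an ITD patient out of the analysis, with SAP 2.2, which adds absent clinical data.

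The cost is a short protocol amendment, a matching SAP edit, and two already scheduled visits in a few patients who would otherwise have stopped.

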4.4 Replacement

Subjects will be replaced under the following conditions:

• Subjects who did not receive study drug administration or did not proceed to imaging

4.5 Subject Identification

After the subject provides written informed consent, the site will assign the subject a 7-digit subject number. Subject numbers are to be assigned in a sequential manner using the following format:

```
Digits 1 to 2: Study number "33"
```

Digits 3 to 4: Site number (e.g., "01")

Digits 5 to 7: Sequential subject number (e.g., "001", "002", "003")

For example, the first subject consented at Site 01 is subject number "33-01-001."

Subjects will maintain the same number given at screening for the entire study. If a subject is a screen failure, the number will not be used for any other subject.

